3.9 Period of Observation

After completion of study drug, subjects will enter follow-up and will be contacted regularly by the Investigator or study personnel to collect information about subsequent therapies, disease status, and survival. Subjects will be followed for safety, duration of response (DOR), progression free survival (PFS), and overall survival (OS) until the end of the study, (see below).

Observation Visits:

- End of Treatment visit: Visit to be performed 14 days (± 2 days) from last drug intake or before start of any new anti-cancer treatment whichever is sooner. For subjects who discontinue prematurely before disease progression it must be performed as the last visit.
- Safety Follow Up visit: All subjects will undergo one Safety Follow-up visit 30 days (± 5 days) after the last AFM24 infusion or before start of any new anti-cancer treatment whichever is sooner.
- Long-term Follow Up: Additional follow-up (phone contact) will take place at 3-month intervals (± 2 weeks) after end of treatment visit until death, lost to follow-up- or mutual decision between PI and sponsor to discontinue Long-term Follow Up of the patient, whichever is sooner.
- End of Study: The study will be terminated as soon as all subjects have completed the first Long-term Follow-Up interval, withdrawn, or died, whichever occurs first.

The study will be analyzed and reported once the last subject of the study has experienced at least one of the following:

- Has been treated till at least 4 weeks after the 1st post-baseline tumor assessment
- Disease progression
- Withdrawal from treatment due to a drug related AE
- Fatal event
- Lost to Long-term Follow-Up
- Withdrawal of consent
- Start of other anti-cancer treatment

In case subjects are still being treated with study medication at the primary analysis cut-off date for this study, such subjects will be kept on treatment in the study and data collected will then be reported in an addendum to the final clinical study report (CSR). It will be noted in the final CSR that such a revised report may be provided.

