	
The expansion cohorts may be opened in parallel or subsequently. Based on the findings in the Phase 1 part of the study, additional treatment schedules (i.e., every 2 weeks [q2w] dosing) may be explored in the Phase 2a expansion cohorts.
 
An overview of the study scheme for each subject in weekly and q2w is described in Figure 5 and Figure 6 respectively.
 
For each subject, the study starts with provision of written informed consent, followed by a screening phase lasting up to 21 days. For Phase 2a only, pre-screening will be required for subjects to determine whether eligibility criteria for EGFR expression (for subjects without a positive EGFR test) have been met prior to entering the screening phase (Note: if a positive EGFR test has been performed from a subject's tumor tissue, and the EGFR laboratory report is available, the subject can proceed directly to the screening activities). Following the up to 21-day screening phase, eligible subjects will be treated with AFM24 administered as an i.v. infusion for as long as they continue to show clinical benefit, as judged by the Investigator, or until disease progression, intolerable toxicity, Investigator discretion, subject withdrawal of consent, or other discontinuation criteria are met.
 
After the end of treatment, subjects will be followed for duration of response (DOR), progression-free-survival (PFS) and overall survival (OS) until the end of the study, which is defined as the date the last subject ending treatment has completed the first Long-term Follow-Up interval.
 
To minimize the number of subjects treated at potentially subtherapeutic dose levels in the dose escalation phase (Phase 1), cohorts 1 and 2 will enroll minimum 2 subjects, whereas cohorts 3 and above will enroll 3 to 4 subjects. In cohorts 3 and above, a fourth subject may be enrolled if treatment of the fourth subject is anticipated to begin within 14 days of treatment initiation of the third subject in the cohort. Treatment in each cohort will begin in a staggered approach with at least 7 days between the first dose of the first subject and the first dose of subsequent subjects. After the first subject in each cohort has begun treatment and been observed for at least 7 days, additional subjects within the cohort may begin treatment concurrently.
 
In cohorts 1 and 2, a minimum of 2 subjects in each cohort need to be treated and complete the 28-day dose-limiting toxicity (DLT) observation period before the Safety Review Committee (SRC) may convene and decide on the dose level for the next cohort of subjects. In Cohorts 3 and above, a minimum of 3 subjects in each cohort need to be treated and be evaluable for DLT assessment to allow for a dose escalation decision by the SRC. All subjects who start treatment need to complete the 28-day DLT observation period or experience a DLT before the SRC meeting and dose escalation decision (minimum of 2 patients in cohorts 1/2 and 3 patients in cohorts 3/4). The dose cohorts might be escalated, de-escalated or expanded to up to 6 subjects based on the SRC decision.
 
Dose escalation decisions will be made by the SRC, consisting of the Principal Investigators at each study center and the Sponsor's Medical representative(s), and additional clinical experts, as needed. The BLRM will be assessed for all subjects in the dose-determining set (DDS) consisting of all subjects who received at least 1 dose of AFM24, and either experienced a DLT at any time during Cycle 1 or met the minimum treatment and safety evaluation requirements without experiencing a DLT within Cycle 1. After completion of a given dose cohort, or at any time the BLRM is updated, the decision to dose escalate and the actual dose chosen will be based on the recommendation of the BLRM regarding the highest admissible dose according to the EWOC principle and the medical review of all available clinical, laboratory, and PK data. The outcome of these analyses and the respective datasets will be reviewed by the SRC. The SRC will then decide the dose level selection of the next dose cohort prior to enrollment. In the event of a Common Terminology Criteria for Adverse Events (CTCAE) Grade 5 adverse event (AE) or a second CTCAE Grade 4 AE at least possibly related to AFM24 at any time during Phase 1, the Sponsor will suspend further accrual and the Sponsor will perform a safety analysis that will be reviewed by an ad-hoc SRC meeting to decide on further progression of the study.

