	DOR, and disease control (CR + PR + SD) assessed by 
• Local RECIST v1.1;• Central RECIST v1.1; PFS measured by local and central assessments Overall Survival
Exploratory Objectives	Exploratory Endpoints
Assess the preliminary antitumor efficacy of AFM24, using iRECIST tumor response criteria	OR (CR + PR) assessed by 
• Local iRECIST• Central iRECIST DOR (CR + PR + SD) assessed by 
• Local iRECIST• Central iRECIST
Assess AFM24 pharmacodynamics	
Explore the predictive potential of biomarkers measured in blood and/or tumor tissue in response to AFM24	

ADA = antidrug antibody; AUC_{tau} = area under the concentration-time curve over the dose interval; C_{max} = maximum plasma concentration; C_{min} = minimum plasma concentration; CR = complete response; DLT = dose-limiting toxicity; DOR = duration of response; iRECIST = Response Evaluation Criteria in Solid Tumors for immunotherapy; i.v.= intravenously; MTD = maximum tolerated dose; OR = overall response; PFS = progression-free survival; PK = pharmacokinetics; PR = partial response; RP2D = recommended phase 2 dose; RECIST = Response Evaluation Criteria in Solid Tumors; SAE = serious adverse events; SD = stable disease; TEAE = treatment-emergent adverse events; T_{max} = time to C_{max}.

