4.3 Subject Withdrawal from Study

Throughout the study, treatment with AFM24 may continue until the occurrence of 1 of the following events, whichever comes first:

- Subject withdrawal of consent;
- Disease progression (if initial radiological progressive disease is observed, while the clinical condition of the subject is stable, treatment continuation is allowed at the discretion of the Investigator. If treatment is continued after initial progressive disease, a confirmatory scan should be acquired within 4 to 6 weeks);
- Occurrence of intolerable toxicity;
- DLT during Cycle 1 in the Phase 1 part;
- Subject non-compliance and the need for withdrawal for this reason as assessed by the Investigator; or
- Investigator decision that it is in the subject's best interest to withdraw from the study.

Upon withdrawal from study drug, the reason for withdrawal should be sought and recorded in the subject file and the withdrawal will be captured in the electronic case report form (eCRF). Every effort will be made to complete the End of Treatment visit, the Safety Follow-up visit and for the subject to be followed up every 3 months thereafter. Where a subject withdraws his/her consent to participate in the study, such follow-up assessments cannot be conducted. The management and holding of data around subject withdrawal will be described in the subject ICF.

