9.3.5 Secondary Analyses

9.3.5.1 Phase 1 (Dose Escalation) & Phase 2a (Dose Expansion)

9.3.5.1.1 Efficacy Analyses

All efficacy analyses will be done for Investigator assessed RECIST v1.1 ([Eisenhauer et al., 2009](#); [Schwartz et al., 2016](#)), Investigator assessed iRECIST ([Seymour et al., 2017](#)), Central assessed RECIST v1.1 and Central assessed iRECIST. The local Investigator assessed RECIST is the primary endpoint for the Phase 2a.

9.3.5.1.1.1 Overall Response Rate

Overall response as defined by achieving confirmed CR and/or PR assessed by RECIST v1.1 will be presented by percentage rates and where appropriate the 95% confidence intervals (CIs). Partial or complete response needs to be confirmed with repeated assessment at least 4 weeks after the initial assessment. For changes in solid tumor size waterfall plots will be presented. For all response assessments swimmer plots will be presented. All response assessments will be listed.

9.3.5.1.1.2 Disease Control Rate at Month 3, 6, and 9

Disease control at months 3, 6, and 9, as defined by achieving CR and/or PR and/or SD assessed by RECIST v1.1 will be presented by percentage rates and where appropriate the 95% CIs. Waterfall plots will be presented.

9.3.5.1.1.3 Duration of Response

The DOR defined as time from first assessment of PR or CR to follow-on first assessment of progressive disease will be summarized by descriptive statistics including median DOR and where appropriate the respective 95% CIs. DOR will also be listed.

9.3.5.1.1.4 Progression Free Survival and Overall Survival

Time from first treatment received until disease progression or OS will be summarized by Kaplan-Meier estimates, median PFS/OS and where appropriate the respective 95% CIs. Subjects with no event will be censored at the last available tumor assessment for PFS and at the last timepoint known alive for OS.

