7.7.3 ANALYSIS OF EXPLORATORY EFFICACY ENDPOINTS

Phase 1 (Dose Escalation)

Overall response rate (CR + PR) and disease control rate (CR + PR + SD), assessed by: Local iRECIST; Central RECIST v1.1 and Central iRECIST will be summarized.

In addition, Clinical Benefit Rate will be calculated and summarized. It will be defined similarly to DCR, but additionally requiring for SD to last at least 24 weeks.

Duration of Response (DOR) will be defined as (date of first progression or death – date of first response (unconfirmed))/30.4375. Patients without response will be excluded from the analysis. Patients without progression or death will be censored at the date of the last tumor scan.

Progression-Free Survival (PFS) will be defined as (date of first progression – date of first study drug injection)/30.4375. Patients without progression or death will be censored at the date of the last tumor scan.

Overall Survival (OS) will be defined as (date of death – date of first dose)/30.4375. Patients alive at the end of study will be censored on the last date of observation. Separate analyses for DOR and PFS will be created for local and central assessments. Censoring rules for all time-to-event endpoints can be seen in the table below.

Endpoint	Situation	Date	Censored/Event
Overall Survival	A death is recorded	Date of death	Event
Overall Survival	No death is recorded	Latest available observed date	Censored
Duration of Response	A PD is observed	First date of PD	Event
Duration of Response	No PD is observed, but there is a death recorded	Date of death	Event
Duration of Response	Neither PD nor Death are observed	Date of the last Tumor scan	Censored
Duration of Response	New anti-cancer therapy is started before any event is recorded	Date of the new anti-cancer therapy	Censored
Time to Response	A Response is observed	Date of the earliest (unconfirmed) response	Event
Time to Response	No Response is observed	Date of latest tumor assessment	Censored
Progression-Free Survival	A PD is observed	First date of PD	Event
Progression-Free Survival	No PD is observed, but there is a death recorded	Date of death	Event
Progression-Free Survival	Neither PD nor Death are observed	Date of the last Tumor scan	Censored
Progression-Free Survival	New anti-cancer therapy is started before any event is recorded	Date of the new anti-cancer therapy	Censored

PD = progressive disease

CONFIDENTIAL

Page 18 of 22

Statistical Analysis Plan template version 1.0 dated 27-MAR-2019

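### Protocol 3.9 lets the investigator and sponsor end one patient's long-term follow-up without any criterion, so Phase 2a overall survival can be censored in relation to prognosis

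*Protocol*

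**What the plan says.** **Follow-up for survival.** The protocol synopsis (Methodology) follows subjects after treatment for "progression-free-survival (PFS) and overall survival (OS) until the end of the study". Section 3.9 opens in the same terms, "progression free survival (PFS), and overall survival (OS) until the end of the study", and refers the reader to the text below it.

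**How contact ends.** The Long-term Follow Up item in 3.9 sets telephone contacts every 3 months after the End of Treatment visit. They run until the earliest of death, loss to follow-up, or a "mutual decision between PI and sponsor to discontinue Long-term Follow Up of the patient". Section 4.3 says that every effort will be made "for the subject to be followed up every 3 months thereafter" and names withdrawal of consent as what prevents this. The long-term follow-up notes to Tables 11 and 16 give the 3-monthly contacts with no discretionary exit.

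**End of study.** Section 3.9 states: "The study will be terminated as soon as all subjects have completed the first Long-term Follow-Up interval, withdrawn, or died, whichever occurs first". Section 3.11 has the same three categories.

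**Role and censoring of OS.** Protocol Table 2 lists OS among the Phase 2a secondary endpoints ("PFS measured by local and central assessments Overall Survival") and as exploratory in Phase 1. Protocol 9.3.5.1.1.4 censors subjects without an event "at the last timepoint known alive for OS". SAP 7.7.3 says: "Patients alive at the end of study will be censored on the last date of observation"; its censoring table uses the latest available observed date when no death is recorded. Protocol 5.7 confirms that there is no blinding.

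**The concern.** The stop applies to a single patient and is decided by two parties who can both know that patient's condition. Nothing limits when it may be used or for what reason. Kaplan-Meier estimation treats a censored patient as having the same outlook as those still under observation. If contact tends to end for patients who are doing badly, their deaths drop out and the OS curve is too high. If it tends to end for stable long survivors, the error runs the other way. The SAP gives these stops no category, count or sensitivity analysis, so a reader of the report could not tell them from ordinary censoring.

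There is also a definitional gap. A patient stopped by joint decision before completing the first follow-up interval has not completed it, has not died, and has not withdrawn in any sense that section 3.9 states. Whether that patient holds up the end of the study or counts towards it is left open.

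**Working it through.** **The plan's own figures.** None apply. OS has no hypothesis, target value or powered test, so there is no stated result to reproduce.

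**Text comparison.**

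| Place | When survival follow-up of a patient ends |
|---|---|
| Synopsis, Methodology | End of study |
| 3.9, opening | End of study, subject to the text below |
| 3.9, Long-term Follow Up | Death, loss to follow-up, or joint decision for that patient |
| 4.3 | Best efforts every 3 months; not possible after withdrawal of consent |
| Notes to Tables 11 and 16 | Every 3 months, no discretionary exit |

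Only one place has the discretionary exit, and neither OS censoring rule distinguishes it.

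**Illustration of size.** The 3-month contact interval comes from section 3.9. Everything else is assumed: exponential survival with true median 6, 8 or 12 months, treatment ending at month 2, and a fraction *f* of patients alive at the first contact (month 2 + 3 = 5) being stopped. In the selective case, a patient dying at time T is censored at the last contact before death, 2 + 3 × floor((T − 2)/3). In the non-selective case, the same fraction is stopped at a random one of the first three contacts, whatever T is.

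The share alive at month 5 is 2^(−5/median): 0.56, 0.65 and 0.75 for medians 6, 8 and 12. At a median of 6, therefore, about 44% die before any 3-month contact and cannot be affected.

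Kaplan-Meier medians from 200,000 simulated times:

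| True median | No stops | Selective, f = 10% | 20% | 30% | Non-selective, 10-30% |
|---|---|---|---|---|---|
| 6 | 5.97 | 6.05 | 6.15 | 6.29 | 5.97 |
| 8 | 7.96 | 8.24 | 8.61 | 9.07 | 7.95 |
| 12 | 11.98 | 12.69 | 13.57 | 14.76 | 11.97-11.98 |

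**Sensitivity at a median of 6.**
- If treatment ends at month 3 or 4, the first contact falls at month 6 or 7, at or after the median, and the median does not move.
- If a stop may also fall at the End of Treatment visit itself (month 2), the range becomes about 6.3-7.4.

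**Sampling error for scale.** With n deaths, complete follow-up and an estimated exponential median of 6, the 95% interval is 6 × 2n/χ²(0.975; 2n) to 6 × 2n/χ²(0.025; 2n).
- n = 8 (where Cohort B enrolment stopped): 96/28.85 = 3.3 to 96/6.91 = 13.9 months.
- n = 15 (the planned interim size for Cohort C): 180/46.98 = 3.8 to 180/16.79 = 10.7 months.

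**The case against.** The case against treating this as important is substantial.

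- **The contradiction is soft.** The opening of 3.9 points to the text below it, so the Long-term Follow Up item can be read as qualifying it. A reader might infer that 4.3 also promises OS follow-up to the end of the study. It does not: it promises best efforts at 3-monthly contact and mentions neither OS nor the end of study. Only the synopsis is unqualified. This stands.
- **Larger bias figures do not fit the schedule.** A reader might suppose contact stops one month before death in 10, 20 or 30% of all patients, which turns a 6-month median into about 6.5, 7.2 and 8.2 months. That ignores the 3-monthly contacts and the patients who die on treatment or before the first contact. Even the schedule-based figures take the extreme case in which every stop is the last contact before death.
- **The loss is recoverable.** A reader might infer that the damage cannot be repaired afterwards. Ending scheduled calls is not withdrawal of consent, and nothing in 3.9 bars a later check of survival status.
- **The mechanism is conjecture.** The contacts exist to record later therapies, disease status and survival, so a patient moving to other care is an expected case for contact. Nothing in the documents shows that any stop was made, or that deteriorating patients were chosen.
- **The consequence is small.** OS is descriptive and single-arm. At a 6-month median, sampling error at these cohort sizes dwarfs a shift of 0.1 to 0.3 months. The end-of-study rule, which secures only the first follow-up interval, limits OS more and would remain.

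What these points leave standing is that the rule permits prognosis-related stops, gives no criterion for them, and provides no means of seeing them in the report.

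**Conclusion.** The point holds but is minor. Section 3.9 permits prognosis-related censoring of a Phase 2a secondary endpoint and leaves the end-of-study status of an early-stopped patient undefined. The documents support the possibility of bias. They do not support a claim that it occurred or had a known size or direction.

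Under the stated assumptions, selective stops move the median by about 0.1-0.3 months at a true median of 6, 0.2-1.1 months at 8, and 0.7-2.8 months at 12. The direction is upward only because stops are assumed to precede death. Stops unrelated to prognosis leave the median unchanged. The clause matters most for patients enrolled early, who could be followed well beyond the first interval before the study ends. The primary objective response analysis and the Simon stopping and rejection rules do not use OS and are unaffected.

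**What to change.** **Protocol 3.9.** Replace the patient-level stop with a stop on one common date for a whole cohort or the study. Otherwise continue contact until death, withdrawal of consent or loss to follow-up. This also closes the end-of-study gap for future patients.

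**Patients already stopped by joint decision.** If they have not withdrawn consent, check survival status once at the data cut-off. State how any who were stopped before the first interval count towards the end of study.

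**Report.** Give the number of such patients, with the date and reason for each stop. If there were none, say so.

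**Cost.** One sentence in the protocol, a short listing, and a few extra calls or records checks. No hypothesis, threshold or sample size changes.
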